#### **8.6.5 Verbal Consent for Trainers**

Trainers are study team members as well as secondary research subjects. Trainers will be provided with an information sheet outlining what their participation, as a research subject, will entail – completion of demographic questionnaire, use of audio recording data of consultation and coaching sessions with school partner for research purposes, and use of fidelity checklist data for research purposes. All of these procedures are detailed in the prior protocol sections.

Informed Consent of trainers will be obtained verbally. Trainers are employed at CHOP and will not be paid for their participation as a secondary research participant. A waiver of documentation of consent is being requested for these participants. Verbal consent will be documented internally by the study team. A study team member other than a principal investigator will obtain verbal consent to prevent coercion.

Given that these participants are research study team members providing a service as a part of this study, the audio recording and completion of fidelity checklists will not be voluntary. Completion of fidelity checklists and audio recording is a widely accepted, standard practice in the delivery of a behavioral intervention to monitor adherence to an intervention manual. These checklists and recordings will be used in the clinical supervision of trainers when applicable.

The use of the fidelity checklist data and audio recordings for research purposes (beyond use in clinical supervision) will be voluntary. Completion of the demographic form for research purposes will also be voluntary. Participants will be given time to ask questions and make an informed decision regarding their completion of the demographic questionnaire and use of the “data” from the fidelity checklists and audio recordings for research purposes. The fidelity checklists, audio recordings, and demographic form (used for research purposes) will not have a negative impact on the trainer’s employability at CHOP. If a trainer declines participation as a secondary research participant, the fidelity checklists and audio recordings will ONLY be used for purposes of clinical supervision. This data would not be analyzed for research purposes.

#### **8.7 Payment to Subjects/Families**

**Parent/Legal Guardian/Caregiver Stipends.** All parents/legal guardians/caregivers completing measures will be given a stipend of \$30 for completing assessment forms at each time point. Forms will be collected at four time points: baseline, post treatment, 5-month follow-up and 12-month follow-up.

**Student Compensation.** Student participants will receive small prizes (valued at \$2 or less) for actively participating in study sessions and for completion of measures at four time points: baseline, post-treatment, 5-month follow-up and 12-month follow-up.

**Teacher Stipends.** Teachers of participating students will be given a stipend of \$30 per student for completing assessment forms at each study assessment time point. Forms will be collected from all participants at baseline, post-treatment, 5-month follow-up, and 12-month follow up.

---

**School Staff Buyout Time.** For their work collaborating with us in conducting the OST-S groups, school partners' time will be bought out so that the school can pay for replacement staff during this time. Our budget calculations assume that for each OST-S group, a school partner will work with us 4 hours a week during the 8 weeks of the OST-S group, running two group sessions a week, preparing for the group, consulting with teachers and parents and meeting with study team trainers for consultation and coaching. In addition, we are assuming that each year they run groups, school staff will spend up to 8 hours in training during the weeks prior to running the first of the two groups. We have also allocated 4 hours per group for both OST-S and TAU groups to compensate the time that they spend assisting in the eligibility assessment and consent process (contacting families).

**School Partner Stipends.** In addition to school staff buy-out, school partners in both conditions will be compensated \$50 for their effort in assisting with student recruitment of two OST-S groups (up to 4 students each) (contacting families, collecting referral forms from teachers, and collaborating with CHOP staff). The stipend will be provided to the school partner each year after the eligible students are enrolled for that particular school year. If two school partners assist with the recruitment of students each school partner will receive \$25 for assistance in recruiting one OST-S group (up to 4 students).

In addition, a stipend of \$25 will be provided to the school partners in both conditions at each of the 4 data collection time points to compensate them for assisting CHOP staff in collecting data from teachers, parents, and students within the school per OST-S group. This often requires additional time and effort on behalf of the school partner to coordinate student and teacher schedules in collaboration with CHOP staff. The stipend will be provided to the school partner after all data from a time point for the OST-S group has been collected (i.e. baseline, post-treatment, 5 Month, and 12 Month.)

For school partners who are in a school assigned to the OST-S Condition only, school partners will be compensated \$50 per group at two different times during the delivery of the OST-S intervention (mid-intervention and at the end of the intervention). This compensation is for the assistance of the school partner for data collection for research purposes that occurs during the OST-S groups.

School partners will also be reimbursed (nontaxable) for travel expenses in the case that they have to travel to a location (other than their own school) for the initial in-service training as described above in Section 3.1.2

Stipends for all participants will be issued on an electronic bankcard that functions like a debit card. Participants will be informed that their personal information to register the card will be shared with the bank institution.

Trainers will not be compensated for their role as a secondary research participant.

## 9 PUBLICATION

We will disseminate information to researchers and practitioners in school psychology, school mental health, special education, and clinical child psychology through conference presentations and publications in peer-reviewed journals. Conferences targeted include National Association of School Psychologists, Council for Exceptional Children, Association

---

for Behavioral and Cognitive Therapies, and Advancing School Mental Health. Journals to target include Journal of School Psychology, School Psychology Review, School Mental Health, Advances in School Mental Health Promotion, Exceptional Children, and Journal of Special Education. Further, the investigators are frequently asked to present to school districts. We will highlight the results of this study in these presentations. In addition, a summary of study results will be posted on the “Resources” section of the CHOP ADHD Center website, as well as on the NYU Child Study Center “About Our Kids” website. Lastly, in collaboration with CHOP Public Relations, we will publicize the results to parents, teachers, and intervention providers through press releases and notifications on the CHOP Facebook page and Twitter feed.

Evaluation of Organizational Skills Training (OST)
Program for Upper Elementary Students

NCT03443323

June 5, 2022

Data Management and Analysis

Analyses followed the intention-to-treat (ITT, as randomized) principle to examine the effect of OST-T2 at post-treatment and follow-up. Time zero was established as the date of consent. All measures were scored according to published instructions, and mean item scores were used in analyses. If an item was missing, mean item scores for each scale were computed without the missing item. An examination of pre-specified baseline student-level covariates, indicated in Table 1, noted some imbalances between groups. For this reason, we rebalanced the data using inverse probability of treatment weights derived from a logistic regression with treatment assignment as the outcome and all covariates as predictors (Loux & Huang, 2023). Once weighted, the baseline covariates collectively produced no association with treatment assignment (Model $p = 0.99$). This balancing procedure was then used in all outcome models to adjust for student-level covariates.

The pattern of medication use to treat ADHD symptoms was similar across conditions. Caregiver-reported rates of student medication use at baseline were 18% for the OST-T2 condition and 23% for TAU/WL; rates were 14% for OST-T2 vs. 18% for TAU/WL at post-treatment, and 16% vs. 21% at 12-month follow-up. Overall, only 9% of students in each condition had a change in medication status at any point in the trial. As such, medication status was not controlled in the analyses.

Prior to analyzing outcome data, we found that actual administration dates of assessments (a) departed frequently from pre-specified times within each assessment period, (b) varied by the informant completing the assessments (caregivers, teachers), (c) varied between treatment arm, and (d) overlapped so that post-treatment data for some students were sometimes collected later than the 5-month follow-up data for others. Discrepancies in data collection from pre-specified times generally were due to variations among informants in response to data requests. For that reason, we preplanned to model time as a continuous variable and allow for non-linear effects of treatment assignment by means of restricted cubic splines with knots at pre-specified locations (Fitzmaurice et al., 2011).

Linear mixed effects models were used to estimate the effects of OST-T2 on outcomes. Models had three levels: assessment time nested within student and students nested within school. All models included time (as splines), treatment, and time-by-treatment interactions. Mixed effects models included random intercepts for school (to account for clustering of students within schools), random slopes (over time) to allow for different trajectories across schools, and a random intercept and random slope for student to allow for variation in the effect of treatment assignment across students over time. Modeling for the clustering effect of schools accounted for more than one student being rated by multiple teachers; teachers rated a mean of 1.6 students and approximately 85% of teachers rated three or fewer students at each time point. Statistical significance was evaluated using a threshold p value of .0083, accounting for the estimation of three contrasts of time-by-treatment differences per outcome and two measures per domain (OTMP skills [COSS-P, COSS-T], homework performance [HPC, HPQ-T], and academic performance [ACES, APS]).

Mixed effects models facilitated both the graphic display, and contrasts, of curves depicting the expected values of outcomes over time from time zero until 12-month follow-up for the student with the last data collected. All confidence bounds reflected variances based on the multi-level linear model. To evaluate differences between conditions, we estimated model-based, expected values for outcomes at four preplanned times, 0 (baseline), 14 (post-treatment), 22 (5-month follow-up) and 55 (12-month follow-up) weeks, except for academic grades, which

were estimated for beginning and end of school year. Those actual times were translated into their equivalent values in the models for restricted cubic splines. Expected values were then the product of these times and estimated coefficients from the mixed effects models. The primary overall estimate of intervention effect for each outcome was the between-group difference of the change in expected values (means) from time zero to the prespecified outcome assessment times. The mixed effects models applied in this study assume that missing scores were missing at random, a reasonable assumption given that we also adjusted for student baseline covariates that might explain missed assessments. Analyses used all available scores, consistent with an ITT approach. Sensitivity analyses were conducted to determine whether data collected after the school shutdown due to the COVID-19 pandemic (March 16, 2020) altered study findings.

Mixed effects models were also used to estimate student-level outcomes at each assessment time. We estimated random effects for students and schools to determine model-based estimates, which reflect expected values (average score of the entire group) plus individual random effects (departures of the individuals from average). Statistical theory suggests that model-based predictions provide better estimates of true values than the actual data. Model-based predictions, called “empirical Bayes” estimates, combine individual measures with group-level expected values in a manner that permits individual estimates to derive strength from the group effects (Efron & Morris, 1973). Using these estimates for each student at each assessment point, we categorized all students based on thresholds derived from normative data sets or common-sense scale values on measures. For the COSS-P, COSS-T, HPC, and HPQ-T, thresholds were set at one-half standard deviation below/above the mean of the normative sample to indicate performance within the normal range (for normative information, see masked for review; [name] et al., 2006; [name] et al., 2007), as this corresponds with a medium effect size. For the ACES and APS, threshold values were set at a value reflecting performance at the standard for grade level (3.0) or above. For academic grades, the threshold was set at a value of 3.0 or above.

To estimate the magnitude of the intervention effect, we computed Cohen’s d . This statistic was calculated as the ratio of between-group differences in changes in expected values over time divided by the standard deviation of the combined, unadjusted baseline scores for each outcome measure.

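### Estimated treatment weights are paired with model-based variances, so the stated confidence bounds need not match the sampling error of the weighted difference in change

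*SAP*

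**What the plan says.** All of this is in the SAP, Data Management and Analysis.

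- Trigger: "An examination of pre-specified baseline student-level covariates, indicated in Table 1, noted some imbalances between groups". The covariates were pre-specified; the decision to weight followed the imbalance.
- Method: "we rebalanced the data using inverse probability of treatment weights derived from a logistic regression with treatment assignment as the outcome", with all covariates as predictors.
- Reach: "This balancing procedure was then used in all outcome models to adjust for student-level covariates".
- Outcome model: "All models included time (as splines), treatment, and time-by-treatment interactions", with random intercepts and slopes for school and student. No baseline covariate, lunch-rate or grade-composition term is listed.
- Variance: "All confidence bounds reflected variances based on the multi-level linear model". No robust, bootstrap or weight-estimation correction is described.
- Estimate: the primary overall estimate "was the between-group difference of the change in expected values (means) from time zero to the prespecified outcome assessment times", evaluated at "0 (baseline), 14 (post-treatment), 22 (5-month follow-up) and 55 (12-month follow-up) weeks".

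The SAP does not say whether the weights are raw, stabilised or normalised, or at which level of the mixed model they enter.

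In the Protocol, Section 6.1.1 plans mixed models without weighting. Section 6.1.4 remarks that covariates might improve power. Section 8.1.1 randomises schools within pairs formed on grades and subsidised lunch percentage.

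**The concern.** Weights estimated from the data remove chance covariate differences between the arms. If the covariates predict the analysed quantity, the weighted estimate varies less from trial to trial than an unweighted one. A model-based variance does not see this: it treats the weights as fixed and leaves the covariate variation in the residual. The reported standard error and the real one then differ.

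The bounds and p-values of every outcome depend on this variance, and each contrast is judged at 0.0083 with about 20 schools, where precision is scarce. Because the method was adopted after imbalance was seen, the plan also leaves open what would have been done without it.

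**Working it through.** **1. Threshold.** Three contrasts times two measures per domain: 0.05 / 6 = 0.00833, which reproduces the SAP's 0.0083. The documents give no standard error or interval width, so the variance question was examined by simulation under the null.

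**2. Inputs.** From Protocol Section 6.1.4: 20 schools (10 per arm), 12 students per school (120 per arm), ICC 0.038. Assumed, because the documents do not give them: 8 covariates, covariate ICC 0 or 0.1, and the share R² of the variance of change that the covariates explain.

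**3. Weighted change-score model, normalised weights, model-based variance** (random school effect, REML, 1,500 runs per setting). The ratio is mean model SE divided by true SD; 1.00 is correct.

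| R² | Ratio, covariates not clustered | Ratio, covariate ICC 0.1 | Coverage of 95% normal interval, not clustered |
|---|---|---|---|
| 0 | 1.02 | 0.96 | 94.3% |
| 0.15 | 1.06 | 1.11 | 95.6% |
| 0.25 | 1.13 | 1.20 | 97.2% |
| 0.50 | 1.32 | 1.56 | 98.6% |

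A separate simulation gave about 1.0 at 0, 1.09 at 0.15, 1.10-1.17 at 0.25 and 1.23-1.32 at 0.40, against 0.97-1.03 with covariates in the model.

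**4. Why 15-25% is a useful range.** Suppose the baseline score is among the covariates. With unit variances and correlation ρ over time, Var(change) = 2(1 − ρ) and Cov(change, baseline) = −(1 − ρ), so R² = (1 − ρ)² / [2(1 − ρ)] = (1 − ρ)/2. The Protocol's ρ of 0.7, 0.6 and 0.5 give 0.15, 0.20 and 0.25. Whether baseline is in the weights is unknown, because the SAP's Table 1 is not supplied.

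**5. Level versus change.** A four-time-point model (weeks 0, 14, 22, 55; school and student intercepts and slopes; assumed variance components; 250 runs) gave:
- Covariates explaining 50% of between-student level variance and none of change: ratio 0.96-1.00.
- Covariates also explaining 50% of slope variance: about 0.97 at week 14, 1.00 at week 22 and 1.12-1.14 at week 55. The unweighted ratio at week 55 in the same runs was already 1.09, so part of that is simulation noise.

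**6. What covariate adjustment does.** In the change-score model, mean SE weighted versus adjusted (ratio for the adjusted model 0.99-1.01):
- R² 0.15: 0.143/0.152 = 0.94, so 6% narrower.
- R² 0.25: 0.134/0.150 = 0.89, so 11% narrower.
- R² 0.50: 0.110/0.146 = 0.75, so 25% narrower.
- R² 0: 0.155 against 0.155, no gain.

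In the four-time-point model, covariate main effects left the week-55 SE at 0.1463, the same as unadjusted. Covariate-by-time terms gave 0.1391, and 0.1391/0.1463 = 0.95.

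**7. Degrees of freedom.** With 20 − 2 = 18 between-school df, the critical value rises by 2.101/1.960 = 1.072 at 95% and 2.965/2.640 = 1.123 at 0.0083. At 0.0083, against a weighted analysis with a normal reference, net width is 0.94 × 1.123 = 1.06 at R² 0.15, 0.89 × 1.123 = 1.00 at 0.25 and 0.75 × 1.123 = 0.84 at 0.50.

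**8. Raw weights.** With assignment probabilities near one half, each raw weight is near 2 and the sum is about 2N. If these count as students, the student part of the variance of a school mean halves. With total variance 1, the correct value is 0.038 + 0.962/12 = 0.1182, and the doubled count gives 0.038 + 0.962/24 = 0.0781. The SE ratio is √(0.0781/0.1182) = 0.81, or 1/√2 = 0.71 without school variance. A re-estimated school variance can absorb the shortfall: a fitted value of 0.1182 − 0.0401 = 0.0781 restores 0.1182 in a change-score model. If the SAP's school slopes are linear in time, they can absorb only the part linear in time, which leaves weeks 14 and 22 more exposed than week 55. The ratio could thus lie anywhere from 0.71 to 1.00.

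**The case against.** The strongest reply is that the estimate is a change from time zero. Covariates that predict only how well a student scores cancel out of it, and no document shows that the covariates predict change. This stands: a reader might infer that the bounds are too wide whenever the covariates predict outcome, and step 5 shows that they need not be.

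Second, simply adding covariates as fixed effects would not help. In balanced two-time-point data with R² about 0.25, the main-effect estimate equalled the unadjusted one in all 300 runs (SD 0.157 for both, against 0.143 for weighting and for covariate-by-time terms). Replacing the weights with main effects would therefore lose the adjustment the SAP now has. This also stands, and it determines the form of the fix.

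Third, a reader might expect adjustment to recover much power. Step 7 limits that: at 15-25% the t reference gives back all the narrowing at 0.0083. The t reference is nevertheless needed with so few schools. In a related set of simulations, the adjusted model with a normal reference had error 0.010-0.014 at 0.0083, against 0.004-0.008 with t on 18 df.

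Fourth, a reader might infer that the analysis was steered by results, or that the weights ignore the matching factors altogether. The SAP names baseline imbalance as the trigger, not outcomes, and the covariates were pre-specified. Student grade and area deprivation are collected per student (Protocol Table 1 and the participant-characteristics section) and may be in the weights. What can be said is that the SAP lists no term for school lunch rate or grade composition.

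**Conclusion.** The point holds as a mismatch between estimator and variance. With normalised weights the standard error is too large to the extent that the covariates predict change: about 6-11% at 15% of change variance and 10-20% at 25%, taking the simulations together. It is about right near 0% or when they predict level only. The sizes rest on assumed R², covariate number and clustering. They carry simulation error of about 1/√(2 × 1,500) = 2% per ratio in the change-score runs and 1/√(2 × 250) = 4% in the four-time-point runs.

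Under that scaling the weighting error is conservative, so the documents do not support a reading that weighting inflates false positives. The loss is precision at 0.0083. The direction is not settled by the text, because the scaling is unstated and raw weights used as frequency weights could make some bounds too narrow. As written, the bounds cannot be reproduced.

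**What to change.** - Make the primary model adjust for the pre-specified baseline covariates and for school subsidised lunch rate and grade composition, whatever imbalance is seen. Enter them with covariate-by-time terms, or as ANCOVA on the follow-up scores. If the baseline score is one of the covariates, the ANCOVA form is the natural one, since baseline is already an outcome in the longitudinal model.
- Refer the treatment contrasts to a t distribution with between-school degrees of freedom (Kenward-Roger or Satterthwaite), and say that this offsets much of the narrowing relative to a normal reference.
- If the weighted analysis is kept, state the scaling of the weights and the level at which they enter, and take its variance from a bootstrap of schools that re-estimates the weights in every resample. With about 10 schools per arm that bootstrap is itself approximate.

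The cost is SAP wording, a re-run of existing models on data already collected, and a few degrees of freedom for the covariate terms. The gain is bounds that match the sampling error and an adjustment that does not depend on what the baseline table shows.

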## **6 STATISTICAL CONSIDERATIONS**

### **6.1 Main Study Analysis**

#### **6.1.1 Study Aims**

**Aims 1 and 2: Effect of Intervention on Proximal and Distal Outcomes.** Linear mixed effects models with random intercepts and slopes for school (the cluster), and fixed effects for intervention, time, and time-by-intervention interaction (the estimate of interest) will be applied. Random effects account for inter-school variation in the effect of the intervention over time.

**Aim 3: Mediation Effects.** This aim explores the effect of potential mediating variables (M; OTMP skills, self-efficacy) on the effect of the intervention (A) on student academic outcome (Y). Our goal is to understand the mechanism of change in student performance due to the planned intervention. In this context, we will examine two levels of mediation: school-level average organization skills associated with school-level academic performance, and student-level organization skills and performance.

**Aim 4: Association Between Fidelity/Engagement and Outcomes:** To determine whether fidelity and engagement are associated with outcomes, we will describe the impact of these factors on outcomes, with special attention to variation in outcomes across schools. These associations will not benefit from randomization (fidelity and engagement are post randomization interim process endpoints). For that reason, our assessments will be largely descriptive and qualitative, and will include assessment during the follow-up periods.

**Aim 5: Effect Modification:** Aim 5 explores potential moderating variables (i.e., gender, grade level, family SES, special education status, and severity of ADHD, externalizing and internalizing behaviors). Because these potential effect modifiers vary within the unit of randomization (school), these contrasts are essential within-cluster comparisons with good statistical power (see below). Effect modification can be estimated using the mixed effects and longitudinal models outlined previously.

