**Aim 6: Cost and Cost Effectiveness.** We will estimate the incremental costs and incremental cost effectiveness (ICE) of OST-S. An ICE ratio will be constructed for each outcome measure with effects that differ significantly from the control group. The ICE will be determined based on differences in direct costs and will be calculated based on differences in mean costs for each condition, divided by the mean difference in outcomes (e.g. ratings of organizational skills and academic performance).

In many OST-S schools, the same school partner will provide intervention during both years of participation. In addition, we expect that many teachers who receive consultation during the first time will be involved again the second time. It is possible that school partners and teachers will be more effective in implementing OST-S later in the study than earlier, which could have some effect on outcomes. Our team will perform sensitivity analyses to determine whether response to intervention in OST-S schools differs for students enrolled earlier versus later in the study.

We anticipate that some of the students in the study will be medicated for ADHD. Medication status did not moderate outcomes for students included in study of OST-C ([name], et al., 2014). During baseline, post-treatment, and follow-up assessments, we will obtain information about student medication status. In the analyses, we will explore whether medication status has an effect on outcomes.

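### The protocol's planned look at whether ADHD medication status affects outcomes has no counterpart in the SAP, and similar use across arms does not answer that question

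*SAP*

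**What the plan says.** Protocol section 6.1.1 (Study Aims, closing paragraph) expects some students to be medicated for ADHD and provides for the data: "During baseline, post-treatment, and follow-up assessments, we will obtain information about student medication status". It then commits to using them: "In the analyses, we will explore whether medication status has an effect on outcomes". The same paragraph notes that medication did not moderate outcomes in the earlier clinic-based study, and makes the commitment all the same.

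The SAP (Data Management and Analysis) treats medication descriptively. Its premise is that "The pattern of medication use to treat ADHD symptoms was similar across conditions". The figures given are:

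- Baseline: "Caregiver-reported rates of student medication use at baseline were 18% for the OST-T2 condition and 23% for TAU/WL".
- Later: "rates were 14% for OST-T2 vs. 18% for TAU/WL at post-treatment, and 16% vs. 21% at 12-month follow-up". No 5-month rate is given.
- Switching: "only 9% of students in each condition had a change in medication status at any point in the trial".

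From these it concludes: "As such, medication status was not controlled in the analyses". The rest of the SAP describes no covariate, stratified, moderator or sensitivity analysis by medication. Its only sensitivity analysis concerns data collected after the COVID-19 school shutdown.

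**The concern.** Two questions have been merged. The SAP's reason addresses whether medication could distort the comparison between arms, and for that question similar use and rare switching are relevant. The protocol asked something else: whether medication status has an effect on outcomes. Two arms can have identical medication rates while medicated students improve more, or less, than others, or while the intervention works only in one of the two groups. Balance says nothing about either.

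At stake is a planned secondary answer. This trial enrols students regardless of diagnosis and treats them in school groups. The clinic study that found no moderation enrolled children with ADHD and treated them individually. The earlier result therefore does not settle the matter here, and the trial already holds the data to examine it.

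**Working it through.** **Step 1. Commitment against delivery.** The protocol promises collection at baseline, post-treatment and follow-up, plus an exploration of effect. The SAP shows that the data were collected and gives rates for three of the four assessments. It contains no exploration of effect and no reason for dropping it; the reason it gives concerns adjustment.

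**Step 2. How large is the baseline difference?** Inputs: 18% and 23% (SAP). The SAP gives no counts per arm, so 140 per arm is assumed from protocol section 6.1.4.

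- Standardized difference = 0.05 / √[(0.18×0.82 + 0.23×0.77)/2] = 0.05 / 0.403 = 0.12.
- Pooled test without clustering: SE = √(0.205×0.795×2/140) = 0.048; z = 0.05/0.048 = 1.04; p = 0.30. The 95% interval for the difference is about −4 to +14 points.
- With 100 to 140 students per arm and design effects of 1.0 to 1.49 (assumed ranges), p runs from 0.30 to 0.47.

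The difference is small and compatible with chance.

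**Step 3. What bias could it cause in the SAP's contrast?** The SAP estimates the between-group difference in change from time zero. If being medicated shifts a score by a constant g SD, in both arms and at all times, only unequal changes in medication rate matter:

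bias = g × [(change in rate, intervention) − (change in rate, control)]

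- Post-treatment: (0.14−0.18) − (0.18−0.23) = −0.04 + 0.05 = 0.01. For g = 0.2, 0.5 and 1.0 (assumed) the bias is 0.002, 0.005 and 0.01 SD.
- 12 months: (0.16−0.18) − (0.21−0.23) = −0.02 + 0.02 = 0. The bias is about zero.
- 5 months: cannot be computed, as no rate is reported.

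The rates are whole percentages. If all four were rounded by half a point in the least favourable direction (4 × 0.5 = 2 points), the post-treatment figure would be 3 points, or 0.03 SD at g = 1.0. The protocol's planning effect is 0.5 SD.

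A larger bias needs a different assumption: that baseline-medicated students *change* differently by d SD whichever arm they are in. Then bias = 0.05 × d, or 0.015 to 0.05 SD for d = 0.3 to 1.0, which is 3% to 10% of 0.5 SD. Nothing in the documents supports a value of d. Estimating it is part of what the missing exploration would do.

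**Step 4. What could the exploration show?** At the planned size about 0.18×140 = 25 and 0.23×140 = 32 students would be medicated, or 57 of 280 (about 20%). Protocol section 6.1.5 claims over 85% power for a 0.67 SD interaction with a modifier at 25% prevalence. Scaling to 20.5% by the modifier's variance, p(1−p): 0.67 × √(0.1875/0.163) = 0.72 SD. Only a large modifying effect would be detected reliably, so an estimate with an interval is the suitable output.

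**The case against.** The best defence is that the SAP sentence is about adjustment, and as such is sound. Arms with similar use and little switching need no medication term in the primary model, and the protocol promised to explore, not to adjust. The SAP also does not hide medication: it reports use by arm at three times. And it is silent on mediation, moderation, fidelity and cost as well, so the gap may only reflect the SAP's narrow scope. Most of this stands. It supports leaving the primary models unchanged. It does not explain the missing exploration, because the SAP takes up medication explicitly and closes the topic on a ground that does not address the protocol's question.

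A reader might infer more than the documents support:

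- *That the primary result is biased.* Step 3 shows otherwise under a constant effect. The documents nowhere state that medication acts on these outcomes. The gap running the same way at every time is not repeated evidence, since these are the same students and 91% never changed status.
- *That the SAP is inconsistent in weighting for other imbalances but not this one.* The table of covariates is not available, so the imbalances that prompted weighting cannot be compared with 18% vs 23%.
- *That adjustment would bring a sizeable precision gain.* Figures such as 4% to 14% of variance explained (medication effects of 0.5 to 1.0 SD, assumed) apply to score levels. The contrast is in change, and the models already carry a random intercept and slope for each student.
- *That the ADHD-severity moderator is distorted.* The protocol's Aim 5 lists "special education status, and severity of ADHD, externalizing and internalizing behaviors" among its moderators, but the SAP contains no such model to correct, and no passage says that baseline ratings describe medicated behaviour.

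**Conclusion.** The concern holds as a departure from the protocol: a stated exploratory analysis was dropped, and the reason given answers a different question. It does not hold as a challenge to the primary result. Expected confounding in the change contrast is about 0.01 SD or less at post-treatment and about zero at 12 months, set against a 0.5 SD planning effect. This rests on three assumptions: a medication effect that is constant over time and across arms, a size of at most 1.0 SD, and reported rates close to the exact ones. The 5-month contrast cannot be checked. The case for action is that the trial can answer a question its own protocol poses at almost no cost, though with limited precision.

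**What to change.** In the SAP's Data Management and Analysis section, replace the sentence on medication. State that the primary models are unchanged, and add two items.

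1. **Sensitivity analysis.** Add baseline ADHD medication (yes/no) to the covariates in the weighting model and refit the outcome models. If it is entered in the outcome model instead, give it its own interaction with time, since a main effect alone does little to a change contrast.
2. **The protocol's exploration.** For COSS-P and COSS-T, fit baseline medication by treatment by time with all lower-order terms. The medication-by-time terms show whether medication predicts change; the three-way term shows whether it modifies the intervention effect. Report estimates with intervals at the preplanned times and label them exploratory. Say that the specification was added after medication rates by arm had been seen.

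Do not adjust for medication after baseline, and do not drop scores after a medication change. Both condition on events after randomization and sit poorly with the intention-to-treat analysis.

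The cost is SAP wording and a few model runs on data already collected. The drawback is a wide interaction interval, which readers should not take as evidence of no modification.
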